Macular pigment optical density (MPOD): Measurements for MPOD will be performed using a non-invasive instrument (*QuantifEye MPS II*, ZeaVision (LLC), Chesterfield, MO) employing well-established psychophysical optical technique based on heterochromatic flicker photometry. ⁷² **Pupil measurement:** Participants' pupil diameters will be estimated while they are exposed to all interventions using a digital video camcorder (model DCR-TRV140, SONY Electronics, Minato, Tokyo, Japan) and subsequent frame-wise analyses using an open-source web application (Pixel

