Ruler, MIOPlanet Technologies, Rimouski, PQ, Canada) that estimates pupil diameter for 5 samples per 15-s video segment. We will then calculate the retinal illuminance. The simplified formula is $T = LS$, where L is the luminance of the stimulus cd/m^2 and S is the area of the pupil in mm^2 . The retinal illuminance T is given in trolands. **Sleep/wake diary:** Subjects will maintain a sleep/wake diary during the entire study. These diaries will document bedtimes, rising times, and caffeine intake. **Actigraphy:** The actigraph is a device the size of a digital wrist watch (1.75" x 1.3" x 0.38", weighing 2 oz) that is worn on the nondominant wrist (Actiwatch, Philips Respironics, Murrysville, PA, or similar). Subjects will begin to wear the device 7 days prior to starting the protocol and throughout the duration of the data collection period. When subjects return to the laboratory for the experimental sessions, the actigraph data will be downloaded and compared to the diary information. Discrepancies will be identified and the actigraph record will be annotated. The data will be analyzed to estimate sleep/wake using the manufacturer's software. **Cognitive tests:** In addition to MOCA (described above), participants will be asked to perform the following tests at recruitment: **Digit Symbol Substitution (DSST):** The DSST requires response speed, sustained attention, and set shifting (executive function). The participant is given 90 seconds to pair correctly numbers with symbols; the higher the score the better the performance. **Digit Span:** Measures working memory's number storage capacity. The participant hears a sequence of numerical digits and is tasked to recall the sequence correctly. Digit span is the longest number of sequential digits that can be accurately remembered. **Verbal Fluency:** Participants have to produce as many words as possible starting with a given letter under various rule constraints. Successful retrieval requires executive control over cognitive processes such as selective attention and inhibition, mental set shifting, internal response generation and self-monitoring.

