Sample Size and Estimated Power. The study will have enough power to detect treatment differences. Previous work by our lab⁷⁴ provides measures of variability for our primary outcome measures (melatonin suppression and questionnaires). In particular, a prior within subjects' study⁷⁴ involving effects of white light on nighttime melatonin suppression have shown that a sample size of 12 or more participants is enough to detect statistically significant ($\alpha = 0.05$) difference in suppression ($\approx 14\%$) for a large effect (Cohen's $d > 0.5$) at a statistical power $\approx 95\%$. A sample size of 19 subjects (24 subjects, 20% attrition) for each group, therefore, should be sufficient for the detection of significant differences in melatonin suppression.

Data and Statistical Analyses

Anticipated Outcomes. Our hypothesis is that greater melatonin suppression will be observed for the on-axis interventions, compared to the off-axis interventions, due to 2 reasons: (1) the greater density of cone photoreceptors in central retina (which will account for about 12% melatonin suppression difference according to CS model calculations⁷⁰) and (2) the *Stiles-Crawford* effect, which suggests that the most effective optical rays incident on the retina are along the foveal axis. Overall, we also expect to see greater melatonin suppression for the low MPOD group compared to the high MPOD group, as higher MPOD means greater attenuation of the photic stimulus. We further hypothesize a significant interaction between the effect of MPOD and light source spectrum, as the yellow macular pigment preferentially filters out short-wavelength radiation, and hence should only attenuate the blue light stimulus. In other words, for high MPOD subjects, we expect to see greater melatonin suppression following exposure to the green light as compared to the blue light exposure. Lastly, we expect to observe a significant interaction between the effect of MPOD and lighting distribution, as since the yellow macular pigment is located primarily in the central retina, the off-axis dose should not be affected by it. Finally, we hypothesize that lower MPOD scores will be associated with lower cognition.

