Overall Analyses will include (1) evaluation to determine data quality, (2) creation of constructed variables and determination of variable distributions, (3) applying tests of parametric statistical assumptions wherever appropriate, (4) preliminary (generally bivariate) testing of hypotheses, (5) consideration of potential covariates to build into the statistical models to increase the probability of detecting treatment effects if they exist, and (6) development and elaboration of multivariate models. SPSS software (V25, IBM, Armonk, NY, USA) will be used for all statistical analyses (significance, $p < 0.05$). [name] will perform all statistical analyses and work with Drs. [name] and [name] on statistical analyses.

Aims 1, 2: In order to evaluate outcomes of the intervention, we will first determine the melatonin suppression for each condition by comparing melatonin levels collected during the dim-light control week to those at the same time in the experimental conditions' weeks. We will then perform a mixed-model analysis of variance (ANOVA), with lighting distribution (on-axis vs. off-axis) and spectrum (blue light vs. green light) serving as the within-subjects factors, and MPOD group (high MPOD > 0.5 vs. low MPOD < 0.3) and cognitive status (MoCA scores) (healthy vs. MCI participants) serving as the between-subjects factors. Mixed model analyses allow for different numbers of observations for different subjects (e.g. if there are dropouts). As sample size and its associated degrees of freedom allow, we will also adjust for covariates that may be associated with outcome measures, such as retinal illuminance, gender, season and any medication load. Within the limits of the sample, we will explore treatment-covariate interactions for each participant-level covariate. If strong interactions are observed, it will suggest that a future study could possibly be stratified on the given factor. To further assess the impact of MPOD on individual light sensitivity, a Pearson correlation coefficient will be calculated between melatonin suppression and MPOD values recorded across MCI patients and healthy older adults. We hypothesize a negative correlation, wherein higher MPOD values will be associated with lower suppression.

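### Adjusting for retinal illuminance, which the lighting condition largely sets, costs precision and can bias the on- vs off-axis and green vs blue contrasts

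*Combined protocol and SAP*

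**What the plan says.** Under Data and Statistical Analyses (Aims 1, 2), melatonin suppression is analysed by a mixed-model ANOVA. Distribution (on- vs off-axis) and spectrum (blue vs green) are the within-subject factors; MPOD group and cognitive status are the between-subject factors. The text then adds: "we will also adjust for covariates that may be associated with outcome measures, such as retinal illuminance, gender, season and any medication load". This step carries a condition, worded as "As sample size and its associated degrees of freedom allow". On interactions, the plan says "we will explore treatment-covariate interactions for each participant-level covariate".

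Under Pupil measurement, retinal illuminance is T = LS, "where L is the luminance of the stimulus" and S is pupil area. On timing: "Participants' pupil diameters will be estimated while they are exposed to all interventions".

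Experimental conditions and Table 1 set blue at 26.7 lux and green at 250 lux, both with a predicted CS of 0.40. On- and off-axis are matched at the eye within each colour. Anticipated Outcomes predicts more suppression on-axis, citing greater central cone density, "which will account for about 12% melatonin suppression difference". It also states that "for high MPOD subjects, we expect to see greater melatonin suppression following exposure to the green light as compared to the blue light exposure".

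The plan does not say whether T enters as one value per condition or one per participant, which luminance is used for L, or whether the adjusted or the unadjusted model is primary.

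**The concern.** Gender, season and medication load are not set by the lighting condition. Retinal illuminance largely is. L is fixed by the condition, and S is measured after the exposure has begun. If T enters per condition, the model is asked to separate the effect of the condition from a variable that nearly encodes it.

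Two harms follow. First, collinearity inflates the standard errors of the within-subject contrasts. Second, the question changes. Aim 1 compares distributions at the same light level, calibrated at the eye, whereas the adjusted contrast compares them at equal trolands. For spectrum, photopic trolands treat green as about nine times stronger than a blue light that was chosen to have the same CS. If suppression rises with T within a condition, the model subtracts a large amount from green, and so works against the plan's own prediction for high-MPOD participants.

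With no primary model named, the adjusted and unadjusted Aim 1 results could disagree with no rule for which counts.

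**Working it through.** **1. The plan's own power figure, used here only to obtain an SD.** Sample Size and Estimated Power says "a sample size of 12 or more participants is enough to detect statistically significant" a difference of about 14 points, at d > 0.5 and about 95% power. A paired t-test with n = 12, d = 0.5 and two-sided 5% alpha gives 35% (49% one-sided), so the figure does not reproduce at that bound. That is a separate matter. Power of 95% needs d = 1.146, so the SD of the paired difference is 14/1.146 = 12.2. At d = 0.5 it is 14/0.5 = 28. Both are carried forward. Completers: 24 × 0.8 = 19.2, so 19 per group and 38 in all.

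**2. Green vs blue luminance.** The geometry is the same for both colours, so L_green/L_blue = 250/26.7 = 9.36. Pupil diameter would have to differ √9.36 = 3.06-fold to cancel this.

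**3. On- vs off-axis luminance (inferred; no cd/m² is given).** Lighting apparatus gives a 30 in. viewing distance, a 22 × 5 in. emitting area, and images of ±5° and ±8–20°. Assume the source is uniformly lit over its full height.
- Illuminance at the eye: E = L ∫ d²/r⁴ dA, with d = 30 in. and height ±2.5 in.
- On-axis: |x| ≤ 30·tan 5° = 2.62 in.; integral 0.02888.
- Off-axis: 30·tan 8° = 4.22 in. to 30·tan 20° = 10.92 in., both sides; integral 0.06522.
- Equal E gives L_on/L_off = 0.06522/0.02888 = 2.26.
- Geometry check: arctan(11/30) = 20.1°, which matches the stated outer edge.

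**4. Assumptions not in the documents.** SD of ln pupil area 0.10–0.30 within person and 0.2–0.4 between; suppression rising 5–15 points per unit of ln pupil area; no pupil response to condition in the base case; 19 participants per MPOD group. Condition then explains 75–95% of the within-person variation in untransformed T.

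**5. The mechanism, on the log scale.** If T entered as ln T with slope γ, the adjusted contrast would be the true contrast minus γ × ln(ratio), with ln 2.26 = 0.815 and ln 9.36 = 2.24. For a true 12-point distribution effect, γ = 5 gives 12 − 4.1 = 7.9 and γ = 15 gives 12 − 12.2 ≈ 0. For green vs blue, γ = 5 shifts the contrast by −11.2. The plan does not specify ln T; this is a worst case.

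**6. Simulation with untransformed T, as the plan defines it.** There were 38 people × 4 conditions and 800–1,500 runs per setting. The model had distribution, spectrum, their interaction and MPOD × each, with and without T, and person as a fixed effect or random intercept.
- *Distribution, true effect 12:* estimated at 7.4–11.8 (fixed) or 6.7–11.3 (random); SE × 1.21–2.05 or × 1.17–1.95.
- *Power for 12 points, SD 12.2:* from 100% to 89–100%.
- *Power for 12 points, SD 28:* each person gives two on–off pairs, so the unadjusted SE is 28/√76 = 3.21 and 12/3.21 = 3.74, or about 95% power. With T this falls to 23–78%.
- *Green minus blue in high-MPOD participants, true value set to +10:* −1.0 to 9.7; SE × 1.35–3.2.
- *MPOD × spectrum and MPOD × distribution:* unbiased when pupils are similar in the two MPOD groups; SE × 0.96–1.01.
- *One nominal L for both distributions:* distribution spared (11.9–12.0, SE × 0.96–1.00), but green minus blue still ranges from −3.1 to 9.9.
- *Pupil constriction added (ln S falling 0.05–0.2 per unit ln L):* SE × 1.37–1.44; distribution estimates 0.9–2.5 points below the unadjusted ones.
- *One pupil value per participant:* distribution estimate unchanged, SE × 0.97–1.00.

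The largest bias and the largest SE inflation arise in different settings. SE × 2.05 goes with within/between SDs of 0.1/0.2, where the estimate is 10.1–11.6. The estimate of 7.4 goes with 0.3/0.2 and slope 15, where the SE is × 1.33. At middle inputs (0.2/0.3, slope 10, SD 12.2) the distribution estimate is 10.3 with SE × 1.44 and power about 100%, and green minus blue falls from 10 to 6.7.

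**7. Separate check.** Generalised least squares with a random intercept, untransformed T, and intraclass correlation 0.3–0.6 gave SE × 1.15–1.95 for distribution and × 1.6–3.65 for spectrum.

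**The case against.** The strongest reply is that the harm depends on one reading. The neighbouring covariates include participant-level ones, and the next sentence speaks of participant-level covariates. If T is one value per person, the within-subject contrasts are almost untouched. This stands as a limit, but the plan does not state that reading, and T as defined takes a different value in each condition.

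Second, the adjustment is conditional and follows a covariate-free ANOVA. Overall Analyses also says covariates are considered in order to raise the chance of detecting treatment effects, a purpose that T would defeat. That is a purpose, not a screening rule. The stated condition is sample size and degrees of freedom, and T costs only one.

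Third, the on/off ratio is inferred, the luminaire figure is not shown, and a single nominal L would spare Aim 1. This stands. The green vs blue part needs only Table 1.

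Fourth, the pupil SDs, the slope and the +10 contrast are assumptions, and SD 28 rests on a bound that is incompatible with the 95% power in the same sentence. This also stands. At SD 12.2 the loss of power is small and attenuation is the main issue.

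Finally, a contrast at equal retinal illuminance is a legitimate question for a project about light at the retina. It is, but it is not Aim 1 as framed and calibrated, so it belongs in a labelled secondary analysis.

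**Conclusion.** The concern holds and should be fixed before analysis. Entered per condition, retinal illuminance is a post-exposure variable set mostly by the factors being tested. The green vs blue distortion follows in direction from the stated lux values, provided suppression rises with pupil area within a condition. Its size runs from almost nothing to about 13 points, depending on pupil variability and slope. The Aim 1 distortion also needs on- and off-axis luminance to differ, as the geometry implies: SE × 1.2–2.05, with a 12-point effect estimated at about 7–12. Whether power suffers materially depends on the SD of suppression, which the plan does not give. The MPOD interactions are largely spared, and the Pearson analyses do not use T. Confidence is high that this is the wrong kind of covariate for the primary model, and moderate about the size of the effect.

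**What to change.** State in the SAP:

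> The primary Aims 1–2 model contains no condition-level retinal illuminance. If pupil size is adjusted for, the covariate is each participant's mean log pupil area over the four light conditions, one value per participant. Trolands are reported by condition descriptively, with the luminance used for L. Any model with condition-level trolands is exploratory and labelled as such.

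The cost is SAP wording only, since the pupil data are already to be collected. The small downside is that pupil differences between conditions are not adjusted for in the primary model. The retinal-dose question is kept as an exploratory analysis.
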